**STUDY DESIGN:**

This study evaluates the safety, PK, and PD of AT-752 and will enroll approximately 60 subjects that meet the inclusion/exclusion criteria. Following screening and informed consent, eligible subjects will be randomized to receive either AT-752 or matching placebo orally 3 times a day (TID) for 5 days in Cohort 1 of the study. Subsequent cohorts will receive AT-752/placebo either twice a day (BID) or TID, as described below. Randomization will be stratified by geographic region. Standard-of-care treatment, including acetaminophen, will be permitted during the study.

At screening, information including demographics, medical history (including time since illness onset), and concomitant medications will be gathered from potential subjects. Any clinical care necessary throughout the study, such as supportive care, will be at the discretion of the investigator and institutional guidelines. Subject eligibility will be confirmed at the screening visit. Randomization and the initial dosing should occur on the same day as screening, if possible. Initial dosing should occur no later than 24 hours after screening.

For TID dosing, subjects will receive doses in the morning, at mid-day, and in the evening. TID doses will be separated by approximately 8 hours. [For BID dosing, subjects will receive doses in the morning and in the evening. BID doses will be separated by approximately 12 hours.] Subjects can continue participation even if hospitalized or using mobile nursing during the study, depending on site availability and subject decision. Subjects will be discharged on Day 6 (after end of treatment) if hospitalized, and asked to return on Day 7, Day 8, and Day 14 ( $\pm 1$  day) with a final safety follow-up performed on Day 28 ( $\pm 3$  days). For clinical sites that decide to use mobile nursing, some of the subsequent visits (Days 2-5,

Days 7-8, and Day 14) may be performed at investigator discretion through mobile nursing. The Day 1, Day 6, and Day 28 visits must be conducted at the clinical site.

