**Figure 3-1 AT-02A-002 Study design**

At screening, information including demographics, medical history (including time since illness onset), and concomitant medications will be gathered from potential subjects. Additional assessments and collection of data will be conducted as indicated in the schedule of events (SOE; [Table 3-1](#)). Any clinical care necessary throughout the study, such as supportive care, will be at the discretion of the investigator and institutional guidelines. After subjects are confirmed eligible at screening, randomization and the initial dosing should

occur within 24 hours, and if possible, the initial dose should be given on the same day as screening.

Upon randomization, subjects will receive their first dose of study drug. Subjects in Cohort 1 will receive doses that are separated by approximately 8 hours ( $\pm 2$  hours; morning, mid-day, and evening). [Subjects receiving BID dosing will receive doses that are separated by 12 hours ( $\pm 2$  hours; morning and evening)]. Subjects can continue participation even if hospitalized or using mobile nursing during the study, depending on site availability and subject decision. Subjects will be discharged on Day 6 (after end of treatment) if hospitalized, and asked to return on Day 7, Day 8, and Day 14 ( $\pm 1$  day) with a final safety follow-up performed on Day 28 ( $\pm 3$  days). For clinical sites that decide to use mobile nursing, some of the subsequent visits (Days 2-5, Days 7-8, and Day 14) may be performed at investigator discretion through mobile nursing. The Day 1, Day 6, and Day 28 visits must be conducted at the clinical site. The Day 6 end of treatment visit will occur 8 to 24 hours after the last dose of study medication is administered.

Note that if the initial dose of study drug is administered on the same day as screening (at mid-day or in the evening), the last dose of study drug will be administered on Day 6. See [Section 3.1.2](#) and [Section 3.1.3](#) for detailed descriptions of TID and BID dosing, respectively.

The 3 planned sequential dosing cohorts are:

- Cohort 1: 750 mg AT-752/placebo TID for 5 days
- Cohort 2: up to 1000 mg AT-752/placebo BID or TID for 5 days
- Cohort 3: up to 1500 mg AT-752/placebo BID for 5 days

In each blinded cohort, subjects will be randomized to receive active drug or placebo in a 3:1 randomization. Each cohort will include 20 subjects (15 subjects receive AT-752 and 5 subjects receive placebo).

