##### 4.1 INCLUSION CRITERIA

A patient must meet the following criteria to be eligible for participation in this study:

1. 18-55 years of age at time of screening
2. Fever  $\geq 38^{\circ}\text{C}$  (or feeling feverish) with onset during the previous 60 hours
3. Positive test confirming DENV on a NS1 antigen test or RT-PCR assay
4. Negative rapid diagnostic test results for SARS-CoV-2 and Influenza A and B
5. Body mass index (BMI) of 18 to 30  $\text{kg/m}^2$

6. Provides written informed consent prior to initiation of any study procedures
7. Able to understand and agrees to comply with planned study procedures and be available for all study visits
8. Males and females of childbearing potential must agree to use protocol-specified methods of contraception as described in [Section 4.1.1](#)
9. Male subjects must agree to not donate sperm from the first dose through 90 days after the last dose of study drug

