#### **8.3.1 Primary Endpoint Analyses**

The primary objective of this study is to evaluate the antiviral activity of AT-752 compared with placebo on change from baseline in viral load (DENV RNA as measured by RT-PCR) based on the log-10 scale at specified timepoints.

Change from baseline in viral load will be compared between each AT-752 arm and the pooled placebo arm. Viral load will be analyzed using repeated-measures mixed model with treatment, time, and treatment-by-time interaction as fixed factors, with more details to be provided in the SAP. The treatment group least squares mean (LSM) estimates for mean change from baseline and treatment group differences at a time point, with 80% CI and p-value will be presented. Additionally, descriptive summaries for the change from baseline will also be presented by treatment group. Further details will be provided in the SAP.

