## **3. Study Design**

### **3.1 Overall Study Design**

This study will enroll approximately 60 subjects in 3 cohorts who meet the inclusion/exclusion criteria. Following screening and informed consent, eligible subjects will be randomized (3:1) to receive either AT-752 or matching placebo either twice a day (BID) or 3 times a day (TID) for 5 days. The dose level for Cohort 1 has been determined on review of PK and safety data from the phase I healthy volunteer study (Protocol AT-02A-001). Specific doses for Cohort 2 and Cohort 3 will be endorsed by a Safety Review Committee (SRC) after an unblinded review of the previous cohorts.

- Cohort 1: 750 mg AT-752/placebo TID for 5 days
- Cohort 2: up to 1000 mg AT-752/placebo BID or TID for 5 days
- Cohort 3: up to 1500 mg AT-752/placebo BID for 5 days

Each cohort will include 20 subjects (15 subjects receive AT-752 and 5 subjects receive placebo). Randomization will be stratified by geographic region. Randomization and the initial dosing should occur on the same day as screening, if possible. Initial dosing should occur no later than 24 hours after screening. Subjects will be discharged on Day 6 (after end of treatment) if hospitalized, and asked to return on Day 7, Day 8, and Day 14 ( $\pm$  1 day) with a final safety follow-up performed on Day 28 ( $\pm$  3 days). For clinical sites that decide to use mobile nursing, some of the subsequent visits (Days 24-5, Days 7-8, and Day 14) may be performed at investigator discretion through mobile nursing. The Day 1, Day 6, and Day 28 visits must be conducted at the clinical site. The maximum duration that any patient will be on study is 32 days.

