#### 4.2. Randomization, Stratification, and Blinding

The randomization schedule will be generated prior to the initiation of the study. Subjects who meet all inclusion and none of the exclusion criteria will be randomly assigned in a 3:1 ratio to either experimental drug or placebo. Randomization will be stratified by geographic region. Randomization numbers (in sequential order) will be assigned before the first dose of study drug is administered on Day 1. This is a double-blind study: the investigator and the subject will be kept blinded to the treatment allocation.

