# **6. Demographics and Baseline Characteristics**

## **6.1 Demographics**

Demographic information collected at screening will be presented in a data listing.

Descriptive statistics will be calculated for the following continuous demographic characteristics:

- Age (years)
- Weight (kg)
- Height (cm)
- Body mass index (BMI) (kg/m^2)

Frequency counts and percentages will be tabulated for the categorical variables:

- Sex
- Race
- Ethnicity

The summaries will be presented by treatment and overall for the safety population.

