### **8.1 Primary Efficacy**

#### **8.1.1 Primary Endpoint**

The primary objective of this study is to evaluate the antiviral activity of AT-752 compared with placebo on change from baseline in DENV viral load (DENV RNA as measured by RT-qPCR) based on the log-10 scale at specified time points:

$$y_i = v_i - v_0$$

where  $v_i$  is the log10 DENV viral load measured at timepoint  $t_i$  and  $v_0$  is the log10 DENV viral load measured at baseline. Viral load measurements that are below the lower limit of quantification (LLOQ) will be set to  $0.5 \times \text{LLOQ}$  in the analysis.

Change from baseline in DENV viral load ( $y_i$ ) will be analyzed with repeated measures mixed model using the method of restricted maximum likelihood (REML). The model will include baseline viral load, treatment, time, and treatment-by-time interaction as fixed factors. An unstructured covariance matrix will be specified for the repeated statement. In case a mixed model with unstructured (UN) covariance matrix fails to converge, a compound symmetry (CS) structure will be used as an alternative. If neither of these converges, independent (ID) structure will be used. If none of these converges, the change from baseline by scheduled time point (ANOVA, Kruskal-Wallis) analysis will be presented as the primary analysis. The treatment group least squares mean (LSM) estimates for mean change from baseline and treatment group differences at each time point, with 80% CI, 95% CI and p-value will be presented.

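### The viral load models leave out time from fever onset to first dose, a baseline value the trial collects, and the SAP does not tabulate it by arm

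*SAP*

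**What the plan says.** Eligibility (Protocol 4.1) requires fever of at least 38°C, "or feeling feverish) with onset during the previous 60 hours". The Estimated Study Duration part of the synopsis ties that limit to screening. A further interval may follow: "Initial dosing should occur no later than 24 hours after screening" (SAP 3.1), with dosing on the screening day preferred.

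Onset time is collected. Protocol section 3 says that "medical history (including time since illness onset), and concomitant medications will be gathered from potential subjects", and Protocol 5.5 has the date and time of each dose recorded.

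The protocol's analysis is a "repeated-measures mixed model with treatment, time, and treatment-by-time interaction as fixed factors, with more details to be provided in the SAP" (8.3.1). The SAP then adds one baseline covariate: "The model will include baseline viral load, treatment, time, and treatment-by-time interaction as fixed factors" (8.1.1). The titre model in SAP section 12 has the same terms. In both models, time means the post-dose time point, not time in the illness.

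Nothing else in the plan brings onset time in:
- Allocation: "Randomization will be stratified by geographic region" (SAP 4.2), and by nothing else.
- Further analyses of the primary endpoint are the per-protocol and as-treated repeats, Kruskal-Wallis and one-way ANOVA by time point, and a Fisher exact test (SAP 8 and 8.1.2).
- The only planned subgroup in SAP section 12 is serotype.
- SAP 6.1 summarises age, weight, height, BMI, sex, race and ethnicity.

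**The concern.** The endpoint is a change from a baseline taken at a variable point in an acute infection. The plan expects virus to clear during follow-up, since it analyses time to clearance in every group, and it restricts entry by time since onset. It is therefore reasonable to expect part of the change in viral load to depend on when in the illness dosing starts.

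Baseline viral load will absorb some of this dependence. It need not absorb all of it, because the same value could be seen while virus is still rising or already falling. That mechanism is an assumption here; neither document states or quantifies it.

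Whatever remains goes into the error term and into chance differences between arms. Each dose arm of 15 is compared with 15 placebo patients, 5 from each of three sequential cohorts, so 10 of the 15 were not randomised alongside that arm. A change over the trial in how early patients present would then enter the contrast systematically. All three dose comparisons share the same pooled placebo group, so a chance gap in that group moves all three. The trial's purpose is dose selection, and no planned by-arm table would show such a gap.

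**Working it through.** **Inputs from the documents.** Onset within 60 h of screening (Protocol 4.1); dosing within 24 h of screening (SAP 3.1); 15 active and 5 placebo per cohort, placebo pooled (SAP 3.1 and 4); one-sided 0.10 test, effect 1 log10, SD 1.25, and an observed 0.5 log10 regarded as suggestive of a signal (SAP 4.1).

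**Assumed, not in the documents.** The spread of onset times (taken as uniform) and the partial correlation r between onset time and change, given baseline viral load.

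**1. The plan's own figures.** By noncentral t, one-sided 0.10, effect 1, SD 1.25:
- 15 vs 15: 81.0% (plan: 80%).
- 15 vs 5: 59.2% (plan: 59%).
- Chance of an observed 0.5 or more with no effect, 15 vs 15, normal: 0.086 at SD 1 and 0.217 at SD 1.75 (plan: 0.09 to 0.22).

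All reproduce.

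**2. Window.** 60 + 24 = 84 h at the outer limit; 60 h if dosing is on the screening day.

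**3. Chance gap in mean onset time, 15 vs 15.** SD of a uniform spread = range/√12. SE of the gap = SD × √(1/15 + 1/15).

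| Spread | SD | SE of gap | P(gap > 6 h) | P(gap > 12 h) |
|---|---|---|---|---|
| 0–60 h | 17.3 h | 6.3 h | 34% | 6% |
| 0–84 h | 24.2 h | 8.9 h | 50% | 18% |

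**4. Effect of a gap on the unadjusted estimate.** The SE of the treatment difference is 1.25 × √(2/15) = 0.456 log10. A gap of one SE in onset time shifts the estimate by r × 0.456. A 12 h gap on the 0–60 h spread is 12/6.32 = 1.90 SE.

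**5. Effect of adjusting.** Residual SD = 1.25 × √(1 − r²). Power is by noncentral t with 27 df. Equivalent arm size = 15/(1 − r²), which does not depend on the SD.

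| r | One-SE shift (log10) | 12 h shift (log10) | Residual SD | Power, 1 log10 | Equivalent n per arm |
|---|---|---|---|---|---|
| 0 | 0 | 0 | 1.25 | 0.81 | 15 |
| 0.2 | 0.09 | 0.17 | 1.22 | 0.82 | 15.6 |
| 0.3 | 0.14 | 0.26 | 1.19 | 0.84 | 16.5 |
| 0.4 | 0.18 | 0.35 | 1.15 | 0.86 | 17.9 |
| 0.5 | 0.23 | 0.43 | 1.08 | 0.89 | 20.0 |

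**6. Form of the covariate.** Viral load is sampled on Days 2 to 8, 14 and 28. Values below LLOQ are set to 0.5 × LLOQ. Once nearly all patients are below it, change equals a constant minus baseline, and onset time can explain nothing beyond baseline. An effect present on Day 3 must therefore fade by the late visits. A single coefficient forces it to be the same at every visit; an interaction with visit does not.

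**The case against.** The case against has real weight.

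- Covariate choice is discretionary. Randomisation makes the within-cohort comparison unbiased on average, and confidence intervals already allow for chance imbalance. SAP section 4 calls intervals and p-values descriptive. This stands, except that pooled placebo patients from other cohorts are not concurrent controls, so randomisation does not protect that part of the contrast against drift.
- A reader might infer that the sample size is wrong because it ignores illness timing. It is not. The figures reproduce, and the planning SD of 1 to 1.75 is a total SD that can already contain this variation.
- A reader might infer that a serious imbalance is likely, or that onset times really spread over 0 to 84 h. The documents support neither. Same-day dosing is preferred, and on the 0–60 h spread a gap above 12 h occurs in about 6% of comparisons. No shift in the table above reaches 0.5 log10.
- The power gain applies a correlation given baseline to an SD not adjusted for baseline, so the absolute power values are illustrative. This stands; the equivalent arm sizes do not depend on it.
- A reader might infer that one added covariate would remove the problem. A constant term across visits to Day 28 cannot do that, and recalled onset, which includes feeling feverish, carries error.
- Listings of medical history and individual viraemia profiles are planned, and Protocol 8.3 summarises background variables, though overall. An attentive reader might notice a gap, but no planned table compares arms on it.

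**Conclusion.** The point holds as an inexpensive improvement to the primary analysis, not as an error that invalidates it. A baseline variable that the sponsor uses for eligibility, and already collects, is missing from both viral load models and from the by-arm baseline table.

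The consequence is some lost precision, unadjusted chance imbalance between arms of 15, and exposure to drift through the pooled placebo. The documents give no evidence that drift will occur, and adjusting for onset time would address only drift in that variable.

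The size rests on a correlation that the documents do not give. At r of 0.2 to 0.3 the gain is about 1 to 3 points of power, or 0.6 to 1.5 patients per arm. At 0.5 it is about 8 points, or 5 patients per arm. The absence of a by-arm summary needs no such assumption.

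**What to change.** Before unblinding, and before any unblinded interim review of viral load:

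1. In SAP 8.1.1 and the titre model of section 12, add time from recorded fever or illness onset to first dose as a baseline covariate, with its interaction with visit. Measure it to first dose, because baseline is the last value before dosing.
2. Name the main effect alone as the fallback if the model does not converge, and state where this step sits in the existing sequence of unstructured, compound symmetry and independent covariance.
3. Add time from onset to first dose, by treatment group, to the SAP 6.1 baseline table.
4. State which recorded onset is used (fever or illness) and in what unit, since the documents give no unit.

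Protocol 8.3.1 leaves model detail to the SAP, so this looks achievable in the SAP alone. The cost is one table row and a few degrees of freedom: one coefficient for the main effect, and up to eight more for the interaction if all nine post-baseline visits are modelled. No new assessment is needed if onset is stored with usable precision. Recall error will reduce the gain. Adding the covariate after unblinding would look data-driven.

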### **3.1.4 Timing of Samples for PK, Viral Load, and NS1**

The timing of samples for PK analyses, viral load determination, and NS1 levels are outlined below for TID and for BID dosing. As shown in the tables below, the timing will vary depending on the time of day that the patient received Dose 1 of study medication and how many doses of study medication they received on Day 1.

10. Timing of sample collections for patients who begin TID dosing at different times on Day 1 and thus receive either 3 doses, 2 doses, or 1 dose of study medication on Day 1, are provided in [Table 3-2](#), [Table 3-3](#), and [Table 3-4](#), respectively. In these tables, Day 1 is the day of dosing. Some of the PK sample times are fixed (pre-dose on Day 1, 24 hours after Dose 1), and some are flexible (serial PK samples for TID dosing may be obtained at either dose 7, 8, or 9). Some of the virology sample times are fixed (pre-dose on Day 1, 24 hours after Dose 1, 48 hours after Dose 1, and 8-24 hours after Dose 15). Other virology sample times are flexible, with samples collected anytime on each of 6 days (Days 4, 5, 7, 8, 14, and 28).
11. Timing of sample collections for patients who begin BID dosing at different times on Day 1 and thus receive either 2 doses or 1 dose of study medication on Day 1, are provided in [Table 3-5](#) and [Table 3-6](#), respectively. In these tables, Day 1 is the day of dosing. Some of the PK sample times are fixed (pre-dose on Day 1, 24 hours after Dose 1), and some are flexible (serial PK samples for BID dosing may be obtained at either dose 5, 6, or 7). Some of the virology sample times are fixed (pre-dose on Day 1, 24 hours after Dose 1, 48 hours after Dose 1, and 8-24 hours after Dose 10). Other virology sample times are flexible, with samples collected anytime on each of 6 days (Days 4, 5, 7, 8, 14, and 28).

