## **7.2 PHARMACODYNAMIC ASSESSMENTS**

Temperature readings will be performed at least 4 times daily through the end of treatment (morning, mid-day, late afternoon, and evening; approximately every 4 hours during waking hours). Temperature will be measured orally and recorded in a patient diary (and given to the site coordinator for entry in the eCRF).

A rapid point of care (POC) test for DENV NS1 antigen and a DENV serotype test will be performed at screening. Viral load will be assessed by measuring plasma viremia by viral titre and with a serotype-specific, real-time reverse transcription PCR assay at screening and on Days 1-8, Day 14, and Day 28. DENV NS1 will be measured by ELISA at screening and on Days 1-8, Day 14, and Day 28. See [Section 3.1.4](#) for a description of the timing for collection of these samples.

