#### **4.1. Sample Size**

The sample size for this study is up to 60 subjects and each cohort will include 20 subjects, allocated 3:1 (AT-752:placebo). In Low et al (Low 2014), the observed standard deviations (SD) for VLR, defined as mean change from baseline viral load on days 2,3, and 4, ranged from 0.75 (N=26) to 1.07 (N=24). Taking into account that the VLR endpoint in the study was based on an average of 3 measurements and assuming that there is some correlation between measurements on days 2 through

4, we consider power to detect a true effect at a single time point using a one-sided 0.10 level test (unadjusted for multiple comparisons) with N=15 per arm for SD in a range from 1 to 1.75:

True standard deviation	Effect (log 10 copies/ml) with 80% power (N=15 vs. 15)	Effect (log 10 copies/ml) with 80% power (N=15 vs. 5)
1	0.8	1.1
1.25	1	1.4
1.5	1.2	1.7
1.75	1.4	2.0

Based on the above table, there is 80% power to detect a true treatment effect (versus placebo) on change-from-baseline viral load of 1 log10 at a time point if the true SD is 1.25 for comparison of groups with N=15 each. The analogous power to detect a 1 log10 effect for a within cohort comparison is 59%. Furthermore, if true SD is in the range from 1 to 1.75, the probability that the observed effect would be 0.5 log10 or larger is low (in range from 0.09 to 0.22) if there is no treatment effect, i.e., an observed effect of 0.5 or larger might be considered suggestive of a signal. Interpretation of results will consider the totality of the data.

In the event there is at least one subject who withdraws without post-baseline virology data, with the exception of those who withdraw for safety or tolerability, enrollment may remain open or extended at each dose level/cohort to enroll additional randomization block(s) of 4 patients (3:1) to increase the likelihood that at least 15 active and 5 placebo subjects with evaluable virology data are included in each cohort. Any additional patients will be randomized through the same centralized randomization process. All statistical analysis will be based on actual enrolled subjects.

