### 8.1.2 Primary Endpoint Supportive Analyses

The primary endpoint will also be analyzed using the same method in the as-treated population.

The following viremia descriptively summarized by treatment arm, with comparison method indicated in parentheses:

- Change from baseline in log10 viral load by scheduled time point (Kruskal-Wallis). Along with the Kruskal-Wallis test, a one-way ANOVA will be used to compare treatment effect separately at each time point.
- Proportion of measurements above the lower limit of quantification (Fisher exact)

All viremia data will be listed and individual profiles of viremia over time will be presented for each subject. Viremia levels below the lower limit of quantification will be considered as 0 in the log10 viral load summaries and indicated as BLQ in the listings.

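### If the unstructured covariance fails, the SAP's fallbacks force one variance on every visit, which can make per-visit intervals too narrow at some visits and too wide at others

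*SAP*

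**What the plan says.** SAP 8.1.1 analyses change from baseline in log10 DENV RNA with a repeated-measures mixed model fitted by REML. "The model will include baseline viral load, treatment, time, and treatment-by-time interaction as fixed factors". For the covariance, "An unstructured covariance matrix will be specified for the repeated statement". If that does not converge, "a compound symmetry (CS) structure will be used as an alternative. If neither of these converges, independent (ID) structure will be used". Only if ID also fails does a visit-wise ANOVA/Kruskal-Wallis analysis become primary. Least squares mean differences are reported at every visit with 80% and 95% intervals and a p-value. Values below the limit of quantification (BLQ) are set to half the LLOQ.

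The visits are described only as "based on the log-10 scale at specified time points". Protocol 7.2 has RNA measured "with a serotype-specific, real-time reverse transcription PCR assay at screening and on Days 1-8, Day 14, and Day 28". That makes nine post-baseline visits: Days 2-8, 14 and 28.

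SAP section 12 repeats the UN, CS, ID sequence for viral titre, with descriptive summaries as its last step. SAP section 4 calls intervals and p-values descriptive. As a supportive analysis, SAP 8.1.2 adds that "a one-way ANOVA will be used to compare treatment effect separately at each time point", alongside Kruskal-Wallis tests. Neither document names a heterogeneous-variance structure or a robust standard error, and neither gives an SD by visit.

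**The concern.** CS and ID differ in how they treat correlation, but both assume the same variance at each visit. Each visit's interval is then sized by the average variance over all modelled visits.

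Unequal variances are likely here. Patients clear virus at different rates, so the spread of change can grow during decline. Once patients fall below the LLOQ they all take one substituted value, which removes residual spread.

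The 80% interval corresponds to the one-sided 0.10 level of the sample size section, since (1 - 0.80)/2 = 0.10. At a visit with above-average variance, noise would look like a signal more often than 10% of the time. At a visit with below-average variance, a real effect would be harder to see.

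**Working it through.** **1. The plan's own figures.** SAP 4.1 states its power for one visit, "using a one-sided 0.10 level test (unadjusted for multiple comparisons) with N=15 per arm for SD in a range from 1 to 1.75". Take an effect of 1 log10, SD 1.25 and z = 1.2816.

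- 15 vs 15: SE = 1.25 × √(2/15) = 0.456. Power = Φ(1/0.456 - 1.2816) = 81.8%, or 81.0% with the noncentral t (plan: 80%).
- 15 vs 5: SE = 1.25 × √(1/15 + 1/5) = 0.645. Power = 60.6%, or 59.2% with the noncentral t (plan: 59%).

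The figures reproduce. The range 1 to 1.75 expresses uncertainty about one SD, not spread across visits. It is borrowed below only to set a plausible scale.

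**2. Effect of a common variance.** With complete, balanced data the estimate at visit j is the difference in means. Its true SE is proportional to SD_j, but CS and ID both report an SE proportional to the root mean square (RMS) of the visit SDs. So:

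- coverage at visit j = 2Φ(1.2816 × RMS/SD_j) - 1
- one-sided error at visit j = 1 - Φ(1.2816 × RMS/SD_j)

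For four visits with SDs 1, 1.25, 1.5 and 1.75, RMS = √[(1 + 1.5625 + 2.25 + 3.0625)/4] = √1.969 = 1.403.

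| SD at visit | RMS/SD | Coverage of 80% interval | One-sided error |
|---|---|---|---|
| 1 | 1.40 | 93% | 0.036 |
| 1.25 | 1.12 | 85% | 0.075 |
| 1.5 | 0.94 | 77% | 0.115 |
| 1.75 | 0.80 | 70% | 0.152 |

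With equal SDs the ratio is 1 and coverage is 80%.

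**3. Simulation check with assumed SDs.** Settings: four groups of 15, nine visits, complete data, no baseline covariate, correlation 0.3 or 0.7, 8,000 trials each.

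- SDs of 1.25, 1.5, 1.75, 1.75, 1.5, 1.25, 1, 1, 1 (RMS 1.364): CS covered 0.68-0.69 where the SD was 1.75 and 0.92-0.93 where it was 1. ID agreed within about a point.
- Late visits most variable: the pattern reversed, with about 0.92 on Days 2-4 and 0.68-0.69 on Days 14 and 28.
- A separate variance at each visit: 0.78-0.81 at every visit in every pattern.

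**4. Which visits?** This needs viral kinetics that the documents do not give. The assumed ranges were: baseline mean 6.5-8.5 log10, SD 1.0-1.3; decline 0.8-1.5 log10/day, CV 30-50%; LLOQ 1.5-3.3 log10; no drug effect.

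- In ten scenarios with Days 2-8 modelled, CS coverage on the worst of Days 2-6 was 0.67-0.75, and on the best day 0.85-0.99.
- One further setting inside the same ranges (baseline 8.5, SD 1.3, decline 0.8/day, CV 50%, LLOQ 1.5) gave 1.00, 0.97, 0.89 and 0.80 on Days 2-5 but 0.68 and 0.66 on Days 7-8.

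The size of the distortion is fairly stable. Its location is not.

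**5. Can the unstructured fit fail?** Nine visits need 9 × 10/2 = 45 covariance parameters from about 60 subjects. At a visit where everyone is BLQ, change is a constant minus baseline. Two such visits give each subject the same residual twice, so the matrix is singular at any common baseline slope.

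In unstructured fits under assumed kinetics without a drug effect (five scenarios of 600 runs, not run in SAS), the matrix was singular in 0 of 3,000 runs for Days 2-8, in 0-43% with Day 14 added, and in 38-100% with all nine visits. These rates depend on the assumptions. The share of runs with all 60 subjects BLQ at one or more of the nine visits was 41-100% in one set of settings and 0.5-94% in another.

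**The case against.** The other side has four good arguments.

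- **The harm is conditional.** It needs the unstructured fit to fail. Failure in SAS was not tested, and the fits limited to Days 2-8 were never singular.
- **Errors run both ways.** In the four-visit illustration mean coverage is (93 + 85 + 77 + 70)/4 = 81% and mean one-sided error is (0.036 + 0.075 + 0.115 + 0.152)/4 = 0.095. Precision is redistributed, not lost overall.
- **The direction is not fixed.** A reader might infer that on-treatment intervals would be the narrow ones, with the one-sided level rising to 0.13-0.20 on the worst on-treatment day. Those figures come from assumed kinetics. They mix two visit sets (0.13-0.17 for Days 2-8, 0.15-0.20 for all nine), and other values in the same ranges put the worst visits after treatment.
- **The stakes are limited.** Intervals are descriptive, no decision rule uses them, and visit-wise ANOVA and Kruskal-Wallis results appear beside them.

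All four stand as limits on priority. They do not remove the defect. A descriptive interval should still have its stated coverage. The supportive ANOVA is not adjusted for baseline and does not correct the primary interval. The visit-wise last step of 8.1.1 is practically out of reach, because an ID fit is ordinary least squares and essentially always succeeds.

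A reader might also conclude that visit-wise ANCOVA should replace the mixed model. That goes too far: SAP section 10 justifies the absence of imputation partly by the use of a mixed model.

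**Conclusion.** The point holds as a conditional weakness in SAP 8.1.1 and section 12. If the unstructured fit fails and the variance of change differs by visit, CS or ID gives intervals of the wrong width at individual visits. With an SD ratio of 1.75 between the most and least variable visits, nominal 80% coverage runs from about 70% to 93%. With equal SDs nothing is lost.

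Visit SDs, LLOQ, decline rates and the list of modelled visits are not in the documents. Neither the affected visits nor the chance of reaching the fallback can therefore be stated. Together with the descriptive status of the intervals, this makes it a low-to-moderate priority, worth doing because it is cheap.

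**What to change.** Amend SAP 8.1.1 before unblinding:

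1. Keep the mixed model. Replace the CS and ID steps with structures that allow a separate variance at each visit, for example TOEPH, then ANTE(1) or CSH.
2. If a simpler structure is still needed, use empirical (sandwich) standard errors with a small-sample correction. This option was not simulated here.
3. State that a singular or non-positive-definite covariance matrix counts as non-convergence.
4. List the modelled visits by study day. At any visit where essentially all subjects are BLQ, report the percentage BLQ by arm instead of a model contrast. Timing matters because SAP section 13 lets the sponsor review unblinded data during the study.
5. Optionally, make the last step a baseline-adjusted visit-wise ANCOVA in place of the unadjusted ANOVA.
6. Make the same changes for viral titre in section 12.

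The cost is a few sentences and lines of code. For nine visits, CSH has 9 + 1 = 10 covariance parameters, and TOEPH and ANTE(1) have 9 + 8 = 17 each, against 2 for CS and 45 for the unstructured matrix. Visits that are almost entirely BLQ would have no model-based contrast.
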